## SYNOPSIS

Title:	A Randomized, Controlled, Double-blind Continuation Study Comparing the Long-term Safety and Efficacy of Orelvo (voclosporin) (23.7 mg Twice Daily) with Placebo in Subjects with Lupus Nephritis.
Short Title:	AURORA (AURinia Orelvo Renal Assessments) 2: Aurinia Renal Response in Lupus Nephritis with Orelvo
Study Product:	Orelvo (voclosporin)
Indication:	Lupus nephritis
Phase:	3
Sponsor:	Aurinia Pharmaceuticals Inc.
Study Code:	AUR-VCS-2016-02
Objectives:	
Primary Objective:
 
 
• To assess the long-term safety and tolerability of Orelvo compared with placebo for up to an additional 24 months following completion of treatment in the AURORA 1 study in subjects with lupus nephritis (LN).
 
 
Secondary Objective:
 
 
• To assess the long-term efficacy of Orelvo compared with placebo for up to an additional 24 months following completion of treatment in the AURORA 1 study in subjects with LN.
 

Design:	Prospective, placebo-controlled, double-blind, parallel-group, 24-month continuation study to the AURORA 1 study (AUR-VCS-2016-01).
Treatment:	
Investigational Treatment:
 
Orelvo softgel capsules containing 7.9 mg drug.
 
Subjects who have completed 52 weeks of treatment with study drug and participation in the AURORA 1 study will continue to receive the same treatment as assigned by randomization in the AURORA 1 52-week study (either Orelvo or matching placebo).
 
Subjects will continue to receive treatment with study drug at the same dose administered at Week 52 of the AURORA 1 study.
 
After 12 months treatment in the AURORA 2 Continuation Study (i.e., 24 months treatment in total), subjects with controlled UPCR (in the Investigator's opinion), subjects taking the 23.7 mg (3 capsules) twice daily (BID) dose will be permitted to reduce the dose of Orelvo to 15.8 mg (2 capsules) BID if considered appropriate by the Investigator and after consultation with the Medical Monitor.

	
Where a dose reduction is considered, the following guidance should be considered:
 
  
 AURORA 2: Week 52 Dose	AURORA 2: Reduced Dose	
   
 23.7 mg BID and UPCR <math>\geq</math>1.5 mg/mg	No reduction	
 
 23.7 mg BID and UPCR <1.5 mg/mg	15.8 mg BID	
 
 <23.7 mg BID	No reduction	
  
 
Notes: BID = Twice daily; UPCR = Urine protein creatinine ratio
 
For any subject receiving an Orelvo (or matching placebo) dose of <23.7 mg BID and presenting with 2 consecutive clinically relevant (in the opinion of the investigator) increases in urine protein creatinine ratio (UPCR), a dose increase of voclosporin (to a maximum of 23.7 mg BID) or appropriate rescue therapy per the Investigator's discretion and current treatment guidelines should be considered.
 
All subjects will continue to receive background therapy of mycophenolate mofetil (MMF) and oral corticosteroids, if applicable, starting at the same dose as at the end of the AURORA 1 study. When clinically indicated, subjects are allowed to be completely titrated off of oral corticosteroids; the sites will contact the Medical Monitor if the dose of oral corticosteroids is to be increased.
	AURORA 2: Week 52 Dose	AURORA 2: Reduced Dose	23.7 mg BID and UPCR $\geq$ 1.5 mg/mg	No reduction	23.7 mg BID and UPCR <1.5 mg/mg	15.8 mg BID	<23.7 mg BID	No reduction
AURORA 2: Week 52 Dose	AURORA 2: Reduced Dose								
23.7 mg BID and UPCR $\geq$ 1.5 mg/mg	No reduction								
23.7 mg BID and UPCR <1.5 mg/mg	15.8 mg BID								
<23.7 mg BID	No reduction								
Inclusion Criteria:	
 
1. Written informed consent before any study-specific procedures are performed.
 
2. Male or female subjects who have completed 52 weeks of treatment with study drug in the AURORA 1 study. Subjects who had a temporary interruption and successfully restarted study drug during the AURORA 1 study will be allowed with Medical Monitor approval.
 
3. In the opinion of the Investigator, subject requires continued immunosuppressive therapy.
 
4. Women of childbearing potential must continue to use effective contraception and have a negative urine pregnancy test at Month 12. Two effective forms of contraception must be used simultaneously unless abstinence is the chosen method. Subjects must use effective contraception during the study (see Section 5.4, Adequate/Effective Contraception).
 
5. Subject is willing to continue taking oral MMF for the duration of the study.
 
								
Exclusion Criteria:	
 
1. Subjects unable or unwilling to give written informed consent and/or to comply with study procedures.
 
2. Currently taking or known need for any of the medications or food items listed in Section 7.8, Prohibited Therapy and Concomitant Treatment during the study.
 
3. Subjects currently requiring renal dialysis (hemodialysis or peritoneal dialysis) or expected to require dialysis during the study period.
 
4. A planned kidney transplant within study treatment period.
 
5. Subjects with any medical condition which, in the Investigator's judgment, may be associated with increased risk to the subject or may interfere with study assessments or outcomes.
 
								

Procedures:	
See Schedule of Events for full details of protocol required procedures and applicable visits (and timings). Subjects who have completed 52 weeks of treatment with study drug in the AURORA 1 study and have provided signed and dated informed consent will be entered into this study. Subjects meeting the required eligibility criteria will be registered in the interactive web response system for the AURORA 2 continuation study, using the same subject number assigned in the AURORA 1 study. Subjects will continue to receive either Orelvo or matching placebo as randomized in the AURORA 1 study. Study drug treatment in the continuation study will remain blinded. Dosing of Orelvo or matching placebo in AURORA 2 is detailed in the Treatment section above. All subjects will continue to receive background therapy of MMF and/or oral corticosteroids, if applicable, starting at the same dose as at the end of the AURORA 1 study. When clinically indicated, subjects are allowed to be completely titrated off of oral corticosteroids; the sites will contact the Medical Monitor if the dose of oral corticosteroids is to be increased.
 
All subjects will receive up to 24 additional months of treatment, i.e., maximum 36 months in total (12 months in AURORA 1 plus 24 months in AURORA 2). After 12 months treatment in the AURORA 2 Continuation Study (i.e., 24 months treatment in total), subjects with controlled UPCR (in the Investigator’s opinion), taking the 23.7 mg (3 capsules) BID dose will be permitted to reduce the dose of Orelvo to 15.8 mg (2 capsules) BID if considered appropriate and at the discretion of the Investigator and after consultation with the Medical Monitor.
 
Subjects who permanently discontinue treatment with study drug will be treated at the Investigator’s discretion, and where appropriate in accordance with current guidelines (e.g., American College of Rheumatology (ACR 2012)). Subjects will return for all remaining study visits and assessments unless they have withdrawn consent. Those subjects who have withdrawn consent to complete remaining visits will be advised to return for the End of Treatment/Early Termination Visit.
 
All subjects will have a safety follow-up visit after the last dose of study drug, and an assessment of vital status at 6 and 12 months post study.

Sample Size:	
Subjects will enter this protocol from the AURORA 1 study in order to provide the opportunity of an additional 24 months of treatment (total of 36 months of treatment); no sample size calculation is required.

Statistical Methods:	
Analysis:
 
All statistical summaries and analyses will be undertaken at study closure once the last subject has completed the Visit 24 safety follow-up visit. A complete description of the statistical analyses to be performed will be presented in a Statistical Analysis Plan (SAP).
 
The study will incorporate an unblinded, interim analysis of both safety and efficacy data. The timing of this interim analysis is expected to be 3 months post the final subject final visit of the AURORA 1 study (i.e., when the last subject reaches Visit 16 of the AURORA 2 continuation study).

---

Populations:

The safety analysis set will consist of all subjects who receive at least 1 dose of study drug in the continuation study.

The efficacy analysis set will be based on the intent-to-treat (ITT) principles and will consist of all consented subjects.

Safety Endpoints:

The analysis and summary of the safety endpoints will be conducted on the safety set.

Adverse events will be aggregated by System Organ Class and preferred term and presented as summary tables.

Laboratory values (based on results from the central laboratory), vital signs and other safety parameters will be summarized by visit as absolute values and change from AURORA 1 baseline. Laboratory values outside of defined normal ranges will be summarized.

Efficacy Endpoints:

All the secondary efficacy analyses will be performed on the ITT set. Data for each visit (as well as change from AURORA 1 study baseline as required) will be summarized by treatment group and visit for each secondary endpoint.

The following key secondary efficacy endpoints will be analyzed using the ITT population using logistic regression with terms for treatment group, baseline UPCR, biopsy class and MMF use at baseline (from AURORA 1) in the model.

- Proportion of subjects in renal response at Months 12, 18, 24, 30, and 36.
- Proportion of subjects in partial renal response at Months 12, 18, 24, 30, and 36.

The results will be expressed as an odds ratio (and associated two sided 95% confidence interval [CI]) for Orelvo compared to placebo. Odds ratios greater than unity show the odds of response are greater for Orelvo than for placebo and therefore indicate a benefit of the Orelvo treatment arm.

The proportion of subjects with renal and extra-renal flares (as adjudicated by the CEC) will be analyzed in a similar fashion to the proportion of subjects achieving response.

The following secondary endpoints will be analyzed using a Mixed Effect Model Repeated Measures (MMRM). The MMRM model will include terms for treatment, visit, treatment by visit interaction, and baseline. Results will be expressed as differences between treatment arms (along with the associated 95% CI).

[figure not shown]
- Change in UPCR, eGFR, urine protein, and serum creatinine from AURORA 1 baseline at each visit.
  - Change in immunology parameters (C3, C4, and anti-dsDNA) from AURORA 1 baseline at each visit.
-

---

	

• Change in HRQoL (SF-36) from AURORA 1 baseline at Months 12, 18, 24, 30, and 36.

• Change in SELENA-SLEDAI scores by visit at Months 12, 18, 24, and 36.

 
Healthcare Resource Utilization at Months 12, 15, 18, 21, 24, 27, 30, 33, and 36. Key aspects will be summarized by visit and changes over time will be explored.
 
[REDACTED]
 
[REDACTED]

--	---

---

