#### **1.2.4.2 Lupus Nephritis Clinical Development**

The AURA-LV study (Protocol AUR-VCS-2012-01) was a randomized, controlled, double-blind Phase 2 study comparing the efficacy and safety of voclosporin (23.7 mg BID or 39.5 mg BID) with placebo in achieving remission in patients with active LN. All patients received background therapy with MMF and corticosteroid taper. The duration of the study was 48 weeks with 265 subjects randomized; the study has completed. The primary endpoint of complete remission was defined as: urine protein creatinine ratio (UPCR) of  $\leq 0.5$  mg/mg at 24 weeks (using first morning void [FMV]) and  $eGFR \geq 60$  mL/min/1.73 m^2 or no confirmed decrease from baseline in  $eGFR$  of  $\geq 20\%$ . In addition, patients could not receive rescue medications for LN (defined as  $>10$  mg prednisone/day for  $>3$  consecutive days or  $>7$  days total from Weeks 16-24) to be considered for complete remission.

The 24-week primary endpoint assessment for the AURA-LV clinical study demonstrated that the groups were generally well balanced for age, gender and race, with a trend to higher proteinuria and lower  $eGFR$  data in the low-dose voclosporin arm. The low dose achieved a statistically significant benefit over placebo for the primary efficacy assessment of complete remission at 24 weeks (odds ratio (OR) [95% confidence intervals [CI]] = 2.03, [1.01, 4.05],  $p=0.045$ ), without a statistically significant improvement seen in the high dose. The results were confirmed by 24-hour urine collections ( $p=0.047$ ). Both the low- and high-dose voclosporin were statistically superior to placebo in partial remission, time to complete remission, and time to partial remission. A mean reduction in serum creatinine was seen in both arms (0.2 mg/dL low, 0.1 high;  $p<0.001$ ). In the voclosporin groups,  $eGFR$  fell by a median of 8-9 mL/min by Week 4 and then stabilized over the course of the study. Blood pressure (BP) did not vary by group. The correlation of 24-hour urine protein and using the FMV was assessed from the results of the AURA-LV study demonstrating a high degree of correlation (Pearson Correlation Coefficient = 0.92).

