### 2.1 Dose Rationale

The AURORA 2 study is designed to evaluate the safety and tolerability of Orelvo 23.7 mg BID versus placebo, for an additional 24 months following a treatment period of 52 weeks in the AURORA 1 study. Orelvo and/or placebo are herein referred to as study treatment. Subjects will continue to receive the same treatment as assigned by randomization in the AURORA 1 52-week study (either Orelvo or matching placebo). Subjects will continue to receive treatment with study drug at the same dose administered at Week 52 of the AURORA 1 study (see Section 7, [Study Treatments](#)).

Orelvo 23.7 mg BID will continue to be administered as a fixed dose without the use of therapeutic drug monitoring. After 12 months treatment in the AURORA 2 Continuation Study (i.e., 24 months treatment in total), subjects with controlled UPCR (in the Investigator's opinion), taking the 23.7 mg (3 capsules) BID dose will be permitted to reduce the dose of

Orelvo to 15.8 mg (2 capsules) BID if considered appropriate and at the discretion of the Investigator and after consultation with the Medical Monitor.

Population PK analyses of voclosporin concentrations from the clinical development program (including healthy subjects, subjects with renal impairment, subjects with hepatic impairment, renal transplant, and plaque psoriasis) demonstrated that weight did not have a significant effect on the PKs of voclosporin. The protocol contains provisions for management of dose based on safety concerns, in particular, BP and renal function. The safety data from the use of voclosporin demonstrates that these risks are dose-related, reversible, and can be managed by dose reduction and temporary interruption.

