#### 7.1.1 Orelvo– Study Treatment

Company Code: [REDACTED]

Chemical Name: [REDACTED]

Empirical Formula: [REDACTED]

Generic Name: Voclosporin

Dosage Form: Softgel capsules

Strength: 7.9 mg of voclosporin per softgel capsule

Manufacturer: [REDACTED]

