### 7.6 Orelvo/Placebo Dose Modification

If GI or other disturbances occur with study treatment, then study treatment dosing may be reduced or interrupted, and/or appropriate treatment may be initiated (e.g., addition of a proton pump inhibitor (see [Appendix 6](#)).

After 12 months treatment in the AURORA 2 Continuation Study (i.e., 24 months treatment in total), subjects with controlled UPCR (in the Investigator's opinion), taking the 23.7 mg (3 capsules) BID dose will be permitted to reduce the dose of Orelvo to 15.8 mg (2 capsules) BID if considered appropriate and at the discretion of the Investigator and after consultation with the Medical Monitor.

Where a dose reduction is considered, the following guidance should be considered:

AURORA 2: Week 52 Dose	AURORA 2: Reduced Dose
23.7 mg BID and UPCR $\geq$ 1.5 mg/mg	No reduction
23.7 mg BID and UPCR <1.5 mg/mg	15.8 mg BID
<23.7 mg BID	No reduction

Notes: BID = Twice daily; UPCR = Urine protein creatinine ratio

For any subject receiving an Orelvo (or matching placebo) dose of <23.7 mg BID and presenting with 2 consecutive clinically relevant (in the opinion of the investigator) increases in UPCR, a dose increase of voclosporin (to a maximum of 23.7 mg BID) or appropriate rescue therapy per the Investigator's discretion and current treatment guidelines should be considered.

Dose modifications for background therapy (MMF and corticosteroids) are detailed in Section 7.2, [Drug Dosage and Administration](#).

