Blood Chemistry	Alanine aminotransferase (ALT)	All visits
	Albumin	All visits
	Alkaline phosphatase (ALP)	All visits
	Aspartate aminotransferase (AST)	All visits
	Bicarbonate	All visits
	Bilirubin (direct and total)	All visits
	Blood urea nitrogen (BUN)	All visits
	Calcium	All visits
	Chloride	All visits
	Cholesterol (total, HDL, and LDL)	Month 24 and Month 36
	Creatine kinase	Every 6 months
	Creatinine	All visits
	Gamma-glutamyl transferase (GGT)	All visits
	Glucose	All visits
	Glycosolated hemoglobin (HbA1c)	Annually
	Lactic dehydrogenase (LDH)	All visits
	Magnesium	All visits
	Phosphorous, inorganic	All visits
	Potassium	All visits
	Protein, total	All visits
Sodium	All visits	
Triglycerides	Annually	
C-reactive Protein	All visits	

Test Type	Test Parameters	Collection at Visits
Urinalysis	Complete urinalysis (to include urine protein, creatinine, blood, urine microscopy).	All visits

QMD Ref: [REDACTED]	Effective: 12Aug2019	Governing QMD: [REDACTED]
Confidentiality Statement		
This document is the property of [REDACTED] and may not be duplicated, copied, altered or removed from company without prior approval from [REDACTED] or in compliance with [REDACTED].		

REF: [REDACTED]

		Controlled Quality Management Document	
		Sponsor:	Aurinia Pharmaceuticals
		Protocol Number:	AUR-VCS-2016-02
STATISTICAL ANALYSIS PLAN. PHASE 2-3-4			

Test Type	Test Parameters	Collection at Visits
Proteinuria	FMV will be performed to analyze UPCR. A 24-hour urine may be substituted for FMV if required.	All visits
	FMV	All visits
	24-hour urine	Every 6 months

Test Type	Test Parameters	Collection at Visits
Pregnancy Test	A serum pregnancy test will be performed for females of childbearing potential. Urine pregnancy tests will be done using a dipstick.	Month 12, Month 24, and Month 36 (Serum)
		Month 12, Month 15, Month 18, Month 21, Month 27, Month 30, Month 33 (Urine)

Test Type	Test Parameters	Collection at Visits
Lupus Markers	Anti-double-stranded DNA (anti-dsDNA) antibodies	All visits
	Serum	All visits
	Complement 3 Complement 4	
Special Tests	Estimated glomerular filtration rate (eGFR)	All visits

Additional eGFR tables will summarize changes from last on treatment value to last off treatment value. The slope of eGFR over time will also be summarized. eGFR slope will be assessed from AURORA 1 baseline to Week 4 and then from Week 4 through to the end of AURORA 2.

A listing of all laboratory measurements recorded throughout the study will be presented.

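### The single Week 4-to-end eGFR slope runs across the elective dose reduction from Month 24, so any eGFR regained then flattens the voclosporin slope and could mask slow renal loss

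*Protocol*

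**What the plan says.** SAP 6.12.2 (Laboratory Data) adds a summary of eGFR slope to its additional eGFR tables: "eGFR slope will be assessed from AURORA 1 baseline to Week 4 and then from Week 4 through to the end of AURORA 2". That makes two segments, of which the second covers almost three years.

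The protocol Synopsis and section 7.6 allow a planned dose step within that second segment. Once 24 months of total treatment are complete, subjects on three capsules BID with controlled UPCR "will be permitted to reduce the dose of Orelvo to 15.8 mg (2 capsules) BID if considered appropriate by the Investigator". The guidance row that points to the lower dose is "23.7 mg BID and UPCR <1.5 mg/mg". SAP section 1 repeats the rule and the table, but SAP 6.12.2 does not carry it into the slope.

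On the renal effect, protocol 2.1 names blood pressure and renal function and says the safety data "demonstrates that these risks are dose-related, reversible, and can be managed by dose reduction and temporary interruption". Protocol 1.2.4.2 reports that in the Phase 2 voclosporin groups eGFR "fell by a median of 8-9 mL/min by Week 4 and then stabilized over the course of the study".

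Other SAP displays bear on the same question:
- Section 6.11.2.4 gives an MMRM of eGFR change with treatment-by-visit terms, an LS-mean plot by visit, and a comparison of last on-treatment with last off-treatment values.
- Section 6.9 tabulates prescribed dose changes.
- Section 6.11.4 lists no sensitivity analysis.

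**The concern.** Breaking the slope at Week 4 keeps the early drop on voclosporin out of the later trend. The elective reduction from Month 24 could produce the same kind of shift in the opposite direction, and there the line is not broken. If the renal effect is dose-related and reversible, a subject who reduces may regain part of the early drop. A straight line fitted through an upward step near its end is flatter than the underlying decline. Removing a placebo capsule has no such effect, so this mechanism acts in the voclosporin arm only.

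The primary objective is long-term safety. A flat long-term slope would be natural evidence against progressive renal loss. As planned, a reader of that slope could not tell true stability from slow decline offset by a dose step. Subjects who reduce are still on treatment, so the on-treatment versus off-treatment comparison does not separate them out.

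**Working it through.** The documents state no expected slope or power, so there is no figure of the plan's own to reproduce.

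**Inputs from the documents**
- Capsule strength: "7.9 mg of voclosporin per softgel capsule" (protocol 7.1.1). So 3 × 7.9 = 23.7 mg, 2 × 7.9 = 15.8 mg, and the reduction is 1 − 15.8/23.7 = 33.3%.
- AURORA 2 visits: Months 15 to 36, every three months (protocol 4.1).
- Early drop: median 8–9 mL/min (protocol 1.2.4.2).
- Subjects: 216 in total (SAP 6.1.1).

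**Assumptions**
- AURORA 1 visits at Week 4 and then quarterly. Two other grids are also tried.
- The regain is present in full at Months 27, 30, 33 and 36, and the off-drug Month 37 value is left out.
- For precision only: 108 per arm, random-slope SD 4 mL/min/yr, residual SD 8 mL/min.
- The 90 mL/min ceiling of SAP 6.2.14 is ignored; it would blunt both loss and regain near 90.

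**Step 1: effect on one subject's slope.** With s = 1 after Month 24 and 0 before, the shift per 1 mL/min regained is Σ(t − t̄)s / Σ(t − t̄)².
- For t = 1, 3, 6, …, 36 months, t̄ = 18.08 months and Σ(t − t̄)² = 11.13 yr².
- The numerator is (27 + 30 + 33 + 36 − 4 × 18.08)/12 = 4.47 yr.
- The shift is 4.47/11.13 = **0.40 mL/min/yr per mL/min regained**.
- It is 0.43 if AURORA 1 contributes only Week 4, Month 6 and Month 12, and 0.37 with a denser AURORA 1 grid (Week 4, Months 2, 3, 4, 6, 8, 10, 12).

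**Step 2: effect on the voclosporin arm mean** (quarterly grid, mL/min/yr)

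| Assumed regain | 25% reduce | 50% reduce | 75% reduce |
|---|---|---|---|
| 0 | 0 | 0 | 0 |
| 1 mL/min | 0.10 | 0.20 | 0.30 |
| 2.83 mL/min (one third of 8.5) | 0.28 | 0.57 | 0.85 |
| 4 mL/min | 0.40 | 0.80 | 1.20 |

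**Step 3: what could be masked.** Assume a regain of 2.67 to 3.0 mL/min (one third of 8 to 9). Ranges cover all three grids.
- A true loss of 1 mL/min/yr reads as −0.50 to −0.35 if half the arm reduces, and −0.01 to +0.30 if all reduce.
- A true loss of 3 reads as −2.50 to −2.35, and −2.01 to −1.70.
- A true loss of 5 reads as −4.50 to −4.35 if half reduce, so rapid loss stays visible.

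**Step 4: comparison with sampling error.** The SE of the arm difference in slope is √[(2/108) × (SD² + 8²/S)], where S = Σ(t − t̄)².
- To Month 36, S = 11.13: √[0.01852 × (16 + 5.75)] = 0.635.
- To Month 24, S = 3.59: √[0.01852 × (16 + 17.83)] = 0.79.
- For a 2.83 mL/min regain, the bias is 0.28/0.635 = 0.45, 0.57/0.635 = 0.90 and 0.85/0.635 = 1.34 SE at 25%, 50% and 75% reducing.
- For a 1 mL/min regain with 50% reducing it is 0.20/0.635 = 0.32 SE.
- With slope SD 6 the SE is 0.879, and even 75% reducing at 2.83 mL/min gives 0.97 SE.

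**Step 5: does the remedy recover the slope?** With a true loss of 3.00 and a step of 2.67 after Month 24, the single slope in a subject who reduces gives −1.84 to −2.01 across the three grids. Both a slope stopped at Month 24 and a model with a step term return −3.00.

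**Step 6: what the remedy does not cover.** Protocol 7.6.1 allows interruption or reduction for falling eGFR at any time, with re-escalation on recovery. By the Step 1 formula, 1 mL/min regained and held after Month 12 shifts the Week 4-to-Month 24 slope by 0.69 and the full-period slope by 0.44. After Month 6 the shifts are 0.61 and 0.33. The shorter slope is more sensitive to these earlier changes.

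**The case against.** **The slope's role.** A reader might infer that this slope is the trial's designated test for progressive renal loss, so that the primary safety conclusion is biased. The documents do not support that. SAP 6.12.2 only summarizes the slope, with no model, test or decision rule. The laboratory estimands in SAP 3.1 are means and mean changes at each visit.

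**Other displays.** The MMRM gives an arm contrast at Month 24, before elective reduction can act, and the LS-mean plot would show a step at Month 27. This stands and limits concealment. These displays do not correct the slope, and none separates subjects who reduced from those who did not.

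**Size of the regain.** It is tempting to assume that cutting a third of the dose returns a third of the drop. Protocol 1.2.4.2 gives 8–9 mL/min for the voclosporin groups, which took 23.7 and 39.5 mg BID. A dose 67% higher shows no clearly larger drop. Protocol 1.2.5 reports discontinuation for decreased GFR in 7.9% of low-dose and 5.7% of high-dose subjects. A regain near zero is compatible with this. Protocol 2.1 supports the direction but gives no size.

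**Direction.** Reduction is optional, and rising UPCR can lead to re-escalation or rescue (protocol 7.6), which could offset a regain. The net bias in favour of voclosporin is therefore conditional.

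**Replacing the planned slope.** A reader might conclude that the Month 24 slope should take over. That would drop the last 12 months of a 36-month course and the view of the regimen as used, and Step 6 shows that the shorter slope has its own exposure. This objection also stands, so the remedy should add to the planned slope and leave it in place.

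**Conclusion.** The concern holds as a conditional weakness in a descriptive safety summary. The SAP's long-term eGFR slope crosses a planned dose step without accounting for it. If eGFR is regained after reduction, the voclosporin slope is flattened by about 0.4 mL/min/yr per mL/min regained in each subject who reduces. At a regain of about 2.8 mL/min with 25% to 75% reducing, the arm mean shifts by 0.28 to 0.85 mL/min/yr. That is enough to obscure loss of around 1 mL/min/yr, but not rapid loss.

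The direction rests on the protocol's statement that the renal risk is dose-related and reversible. The size rests on a regain and a share reducing that the documents do not give, and it could be close to nothing. The case for acting is that the safeguard is cheap and lets a reader separate a dose step from true stability.

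**What to change.** In SAP 6.12.2:

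1. Keep the Week 4-to-end slope and label it the summary of the whole regimen.
2. Prespecify beside it, for all subjects in both arms: (a) a Week 4-to-Month 24 slope; and (b) the full-period slope with a level-change term by arm after Month 24. Use the same calendar cut for everyone, so that it does not select on UPCR or on who reduced.
3. State that absence of progressive renal loss will not be concluded from the single full-period slope alone.
4. State that reductions or interruptions for falling eGFR before Month 24 (protocol 7.6.1) can still affect the Month 24 slope, and report by arm how many subjects had them.

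No dosing rule changes and no new data are needed. The cost is SAP wording, a little more analysis, and lower precision in the added slope: SE about 0.79 versus 0.64 mL/min/yr at slope SD 4, 0.64 versus 0.42 at SD 2, and 1.00 versus 0.88 at SD 6.
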